Participants will complete stimulation sessions on Days 1, 3, & 5 (**week 1**). Participants will receive a call instructing them to stop smoking ~18 hours before their tDCS Session 1, tDCS Session 2, and tDCS Session 3 appointment start times (resulting in ~18 hours of smoking abstinence at the start of these visits).

Participants will complete the following prior to the tDCS period:

1. Women of childbearing potential will be provided with a urine pregnancy screen and will be instructed to perform the screening independently. Participants will be instructed that women who think they are pregnant are advised not to participate in the study;
2. BrAC assessment. See breath alcohol concentration under screening/covariates for exclusionary criteria;
3. Carbon monoxide (CO) Breath sample (must be <10 ppm or 50% of intake CO level at Session 1 to participate).
4. Paper and pencil questionnaires (brief QSU-B, G-FCQ-S, smoking TLFB).

**tDCS Training Procedures:** Prior to each tDCS period an investigator or trained research assistant will review the procedures, goals, risks, and potential benefits of the study and confirm that no change has occurred affecting study inclusion and exclusion criteria. The tDCS sessions will be conducted by a trained technician using the neuroConn DC-Stimulator Plus system. Participants will receive sham or active tDCS using the parameters described below. The participant will be blind to condition (sham vs. active and dosage).

Active tDCS: A neuroConn DC-Stimulator Plus will apply a constant direct current (1.0 mA to 2.0 mA via 5x7 electrode) to the left dorsal lateral prefrontal cortex. Each participant will receive anodal stimulation for a period of 20 minutes. For anodal stimulation over the left DLPFC, the anodal electrode will be placed over the left F3 and the cathodal electrode over the right supraorbital area (international EEG 10/20 system).

**Sham tDCS:** During sham tDCS, a 1.0 mA to 2.0 mA current will be delivered for approximately 30 seconds before being extinguished over a course of seconds. Again, the anodal electrode will be placed over the left F3 and the cathodal electrode over the right supraorbital area. Most participants cannot distinguish between real and sham tDCS (Gandiga, Hummel et al. 2006).

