3. After 50 minutes (regardless of whether the participant decided to smoke during the resist period), the 60 minute ad-lib smoking session will commence. During this period, participants will receive \$4.00 at the beginning of the session and will be instructed to "smoke as much or as little as you wish." They will be further instructed that for each cigarette lit, they would "lose \$0.50 from their \$4.00 tab." The primary outcomes will be latency to first cigarette and number of cigarettes smoked during the resist and ad-lib periods.
4. At the end of the ad-lib period, all participants will be asked to smoke one cigarette in order to standardize smoke exposure for subsequent tasks.
5. Participants will complete paper and pencil assessments of craving and a tDCS side effects questionnaire.

At the end of Session 3, smokers will receive a 20-minute in person coaching session and be instructed to try to remain abstinent from 10 P.M. that evening until after the final Monitoring Visit (7 days of monitored abstinence), with small monetary incentives for abstinence and biochemical verification. All participants will be discharged ~4 hours after their appointment start time.

**Monitoring Visits:** (Visit duration ~20 minutes). During the monitored abstinence period, participants will complete 4 Monitoring Visits (days 6, 8, 10, and 12). Participants will be given instructions to remain abstinent from smoking from 10 P.M. the evening of Day 5 until after they complete their final Monitoring Visit on Day 12. On Days 6, 8, 10, and 12, all participants will be asked to come to the CIRNA for brief visits to complete the following:

- Complete CO, smoking rate (TLFB), and concomitant medication assessment.
  - To increase abstinence motivation, participants will receive \$15/day (in cash) for each day of self-reported abstinence that is biochemically-confirmed. On Day 6, a CO reading of less than 10ppm or less than 50% of CO breath sample taken at the Intake session will be sufficient as

biochemically-confirmed abstinence. On Days 8, 10, and 12, a CO reading less than 8 ppm will be considered as biochemically-confirmed abstinence.

- Complete measures of smoking urges (Table 1).

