**Table 1. Measures and Time Points**

Activity	Intake	tDCS Sessions 1-3	Monitoring Visits 1-4
Weeks	-1	0	1
Urine Pregnancy Screen	x	x	
BrAC	x	x	
Time Line Follow Back (TLFB), CO	x	x	x
Demographics	x		
ETOH History	x		
Height	x		
Weight	x		
Medical History Form	x		
Shipley Institute of Living Scale (SILS)	x		
Saliva for DNA (Oragene™)	x		
Saliva sample (for nicotine metabolites)	x		
Smoking Behavior (FTND & Cigarette Brand)	x		
Treatment/Training			
tDCS (1mA, 2mA or sham)		x	
Side effects		x	
Intermediate Outcomes			
Urges/Cravings (QSU-B)	x	x	x
Post-Test Questionnaire		x*	
Primary Outcomes			
Ability to Resist Smoking		x	
Number of Puffs, Cigarettes		x	
Days of biochemically confirmed abstinence			x

\*after session 3 only

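### Does the looser carbon monoxide limit on Day 6 weaken the count of confirmed abstinent days?

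*Combined protocol and SAP*

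**What the plan says.** The CO rules stand in the protocol under Study Procedures, 1. Procedures, Monitoring Visits. For the first visit the text gives "On Day 6, a CO reading of less than 10ppm or less than 50% of CO breath sample taken at the Intake session" as sufficient. For the others it says: "On Days 8, 10, and 12, a CO reading less than 8 ppm will be considered as biochemically-confirmed abstinence". Both rules appear in the bullet on the daily cash incentive, which is paid "for each day of self-reported abstinence that is biochemically-confirmed". Self-report and CO must therefore both indicate abstinence.

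Three other places set the context:

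- **Craving and Smoking Assessment, item 4.** At the end of each laboratory session, including Session 3 on Day 5, "all participants will be asked to smoke one cigarette in order to standardize smoke exposure for subsequent tasks".
- **Monitoring Visits.** Participants are told to "remain abstinent from smoking from 10 P.M. the evening of Day 5 until after they complete their final Monitoring Visit on Day 12". Smoking on Day 5 before 10 P.M. is therefore no breach.
- **tDCS Sessions, item 3.** After about 18 hours of requested abstinence, CO "must be <10 ppm or 50% of intake CO level at Session 1 to participate". This is nearly the Day 6 rule.

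Table 1 lists "Days of biochemically confirmed abstinence" under Primary Outcomes. The statistical analysis paragraph models the total of such days by dose group, with age, sex, race and FTND score as covariates. It states no CO threshold of its own.

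**The concern.** A reading of 8 or 9 ppm counts as abstinent on Day 6 and as smoking on Day 8. A participant with a high intake CO can pass Day 6 at a level far above 8 ppm. Intake CO must be at least 10 ppm, so the Day 6 limit is looser for every eligible participant. Someone who smokes after 10 P.M. and reports abstinence might be confirmed on Day 6 only because of the looser limit, and that day would count the same as one confirmed below 8 ppm.

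If this happened often, it would blur the difference between dose groups in an outcome that Table 1 calls primary. The obvious response would be to repeat the analysis with 8 ppm at all four visits, or without Day 6, to see whether the conclusion changes.

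**Working it through.** The plan gives no figure of its own to reproduce here. The check has four steps.

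**1. How far apart the two rules are.** With intake CO of C ppm, the Day 6 limit is max(10, C/2).

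| Intake CO (ppm) | Day 6 limit (ppm) | Above 8 ppm by |
|---|---|---|
| 10 to 20 | 10 | 2 |
| 25 | 12.5 | 4.5 |
| 30 | 15 | 7 |
| 40 | 20 | 12 |
| 50 | 25 | 17 |

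The gap is real.

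**2. What a compliant participant would read.** The documents give neither a CO half-life nor a visit time. Assume a half-life h of 3 to 8 hours and a 9 A.M. visit, which is 11 hours after 10 P.M. The remaining share is 2^(-11/h): 0.386 for h = 8, 0.218 for h = 5 and 0.079 for h = 3.

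- From 40 ppm at 10 P.M., the Day 6 reading is 40 × 0.386 = 15.4, 40 × 0.218 = 8.7 or 40 × 0.079 = 3.2 ppm.
- From 30 ppm with h = 8, it is 30 × 0.386 = 11.6 ppm.
- A true abstainer fails an 8 ppm limit if CO at 10 P.M. exceeded 8 × 2^(11/h), which is 20.7 ppm (h = 8), 36.8 ppm (h = 5) or 101.6 ppm (h = 3).
- By Day 8, 48 hours later, 59 hours have passed. Even with h = 8 the remaining share is 2^(-59/8) = 0.006, so 40 ppm has fallen to about 0.2 ppm.

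Residual CO from permitted smoking can matter on Day 6 and cannot matter from Day 8 onward. A different limit at the first visit fits this. The Session 1 check has the same pattern, with nearly the same limit when abstinence is counted in hours. The protocol does not state this reason; it is inferred from the timing.

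**3. What a switch to 8 ppm on Day 6 would do.** Let a be the share of true Day 6 abstainers who are confirmed, and l the share of lapsers who are confirmed. With true abstinence shares p1 and p0 in two arms, and a and l equal across arms, the observed Day 6 difference is (a - l)(p1 - p0). Moving to 8 ppm lowers l by f (lapsers no longer passed) and a by g (abstainers now failed). The multiplier a - l therefore changes by f - g. With an equal true effect on every day, the difference in the total changes by (f - g)/4 if visits are counted, or (f - g)/7 if days are counted. The available text does not show which applies.

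| f | g | Change, 4 visits | Change, 7 days |
|---|---|---|---|
| 25% | 0% | +6.3% | +3.6% |
| 25% | 25% | 0 | 0 |
| 10% | 25% | -3.8% | -2.1% |
| 50% | 0% | +12.5% | +7.1% |
| 0% | 50% | -12.5% | -7.1% |

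All values of f and g are assumed; the documents support none of them. The two are also linked. A cigarette just before 10 P.M. is allowed and one just after is a lapse, yet both leave almost the same CO next morning. A limit low enough to catch the second also fails the first.

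**4. Bias between arms.** If p1 = p0, the expected difference is zero under either rule, so the Day 6 limit creates no false effect while a and l are equal across arms. The 50% branch depends on intake CO, which is measured before randomisation and balanced in expectation. The outer bound is one day per participant. If the share reclassified on Day 6 differed by 10 points between arms, the mean difference would move by 0.10 day. At an assumed SD of 1 to 3 days that is 0.10 to 0.03 SD. For scale only, the design effect size quoted in the futility paragraph is 0.45.

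**The case for a change.** The strongest contrary case is this. The two limits differ for everyone, they feed one sum, and Table 1 calls that sum primary. The 50% branch scales with intake CO, which is not among the covariates, so a chance imbalance is not adjusted for directly. CO and smoking diary data exist at all four visits, so two labelled re-runs of the model would cost little.

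The facts stand, and such re-runs would do no harm. They would not settle the question, however. Requiring 8 ppm on Day 6 brings in the opposite error, so a changed result could mean that lapsers were removed or that abstainers were wrongly failed. Dropping Day 6 removes the first visit after the last stimulation session, so a changed result could reflect timing rather than the CO rule. Chance imbalance in a baseline variable is part of the random error that the test already allows for.

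Two premises also cannot be established. The limits are written for the payment. They are the only visible definition of confirmation, but most of the analysis section is missing from the available text, and a separate outcome definition or a threshold sensitivity analysis may stand there.

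Item 3 of the Craving and Smoking Assessment says "The primary outcomes will be latency to first cigarette and number of cigarettes smoked during the resist and ad-lib periods", and Table 1 adds abstinence days. That is a separate question of outcome status. It does not make the CO rule right or wrong.

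**Conclusion.** The concern does not hold. The plan does use a looser CO limit on Day 6. It is a stated rule, identical across arms, confined to one of four visits, required together with self-report, and consistent with a visit that follows permitted smoking by hours. It creates no expected difference between arms where none exists.

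Its possible cost is some loss of contrast. A uniform 8 ppm limit has the same kind of cost in the other direction: for f and g each between 0 and 50%, the net change in the arm difference lies between -12.5% and +12.5% (four visits) or -7.1% and +7.1% (seven days). Neither rule is shown to be better, so no change to the definition would correct an error.

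This rests on an assumed half-life of 3 to 8 hours, an assumed 9 A.M. visit, an equal effect on each day, and misclassification shares that are equal across arms. CO at 10 P.M. is also unknown. Participants were asked to abstain for about 18 hours before Session 3, so it may be well below intake level. In that case fewer compliant participants would fail 8 ppm, and the two rules would disagree less often.

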**Table 1. Measures and Time Points**

Activity	Intake	tDCS Sessions 1-3	Monitoring Visits 1-4
Weeks	-1	0	1
Urine Pregnancy Screen	x	x	
BrAC	x	x	
Time Line Follow Back (TLFB), CO	x	x	x
Demographics	x		
ETOH History	x		
Height	x		
Weight	x		
Medical History Form	x		
Shipley Institute of Living Scale (SILS)	x		
Saliva for DNA (Oragene™)	x		
Saliva sample (for nicotine metabolites)	x		
Smoking Behavior (FTND & Cigarette Brand)	x		
Treatment/Training			
tDCS (1mA, 2mA or sham)		x	
Side effects		x	
Intermediate Outcomes			
Urges/Cravings (QSU-B)	x	x	x
Post-Test Questionnaire		x*	
Primary Outcomes			
Ability to Resist Smoking		x	
Number of Puffs, Cigarettes		x	
Days of biochemically confirmed abstinence			x

\*after session 3 only

### 1. Screening/Covariates:

**Urine Pregnancy Test (females only):** At the Intake and Session 1-3 visits (4 urine pregnancy screens total), participants will be supplied with a simple, CLIA-waived urine pregnancy screen and informed that pregnant women are not advised to participate in this research study. Participants will then be instructed to administer the pregnancy test independently and will inform study staff if they would like to continue participation after they have administered the pregnancy screen. Participants will be informed that there is no penalty for discontinuing participation at this point in the visit and that they will still receive travel reimbursement for the visit.

**Breath Alcohol Concentration:** The BrAC assessment will be administered at all study visits. The breath alcohol monitor is a handheld device that uses a disposable mouthpiece and reports the concentration of alcohol in exhaled breath. Any reading > 0.000 indicates alcohol consumption within the last 14 hours. Participants with a BrAC greater than or equal to 0.01 at the Intake Visit will be ineligible. Participants who have a BrAC reading greater than or equal to 0.01 at either tDCS visit may be ineligible to continue with the visit and will only be rescheduled/allowed to proceed with the study at the discretion of the Principal Investigator.

**Demographics:** Standard surveys will collect demographics (e.g., age, education, race, and gender).

**Medical:** Height and weight will be measured and recorded. All participants will complete a medical history form with a trained staff member to review for all contraindications listed previously.

**Shipley Institute of Living Scale:** All participants will complete the Shipley Institute of Living Scale (SILS) at the Intake Visit. The scale consists of two subtests: a 40-item vocabulary test and a 20-item test of abstract thinking. The total administration time is 20 minutes (10 minutes per subtest). A trained member of the study staff will score

2012; Roche et al., 2014). Similar models were used to estimate the effects of dose group on total number of days of biochemically-verified abstinence during the monitored abstinence period; age, sex, race, and nicotine dependence (FTND score) were included as covariates.

We conducted a futility analysis based on conditional power (futility = conditional power <20%) using results from the mixed model with dose of 1mA and 2mA lumped. Conditional power was calculated using PASS v15 (Power and Sample Size, NCSS Software, Kaysville, UT). Conditional power is the probability of rejecting the null hypothesis given the data already revealed; data that have not been revealed yet are assumed to follow the original assumed effect size. We used the z-score for the comparison of sham with lumped active treatment ( $z=0.04$ ,  $p=0.96$ , effect size=0.01), combined with the original design effect size of  $d=0.45$ . Conditional power was 0.13, indicating that the study should be abandoned for futility (Proschan et al., 2006).

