**Medical/Neuropsychiatric:**

1. Women who are pregnant, planning a pregnancy, and/or breast feeding. All female subjects will complete a urine pregnancy test at the intake visit and preceding all brain stimulation sessions (4 urine pregnancy tests in total). Women who self-report a condition which renders them unable to become pregnant (i.e., hysterectomy, surgical sterility, menopause, etc) will not be required to complete the pregnancy tests;
2. History of epilepsy or a seizure disorder;
3. History of stroke;
4. Self-reported history of brain or spinal tumor;
5. Self-reported history or current diagnosis of psychosis, including schizophrenia, mania, bipolar disorder, major depression (subjects with a history of major depression but in remission for past 6 months are eligible).

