**tDCS-related:**

1. Self-report of metallic objects in the face or head **other than** dental apparatus (e.g. braces, fillings, and implants);
2. Self-report of pacemakers or implantable cardioverter-defibrillator (ICD).
3. Self-report of any skull fracture or opening.

**Note:** In contrast to Transcranial Magnetic Stimulation (TMS), there is no known risk of seizures with tDCS. However, the individuals with self-reported history of epilepsy, a seizure disorder, or any seizure in the last 6 months will be excluded. Similarly, although there is no known risk of tDCS to the fetus, the issue has not been fully addressed. Consequently, pregnant women will be excluded. All women of childbearing age (that is, not post-menopausal, surgically sterile, or otherwise unable to become pregnant) will complete a pregnancy test prior to each tDCS session.

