***5. Vulnerable Populations***

Children (under age 18), pregnant women or prisoners are not included in this research study.

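### Pregnancy is an outright exclusion, but the test procedure is advisory and never makes a positive test disqualifying

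*Combined protocol and SAP*

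**What the plan says.** The exclusion appears in three places in the combined protocol and SAP.

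- The Medical/Neuropsychiatric exclusions, item 1, list "Women who are pregnant, planning a pregnancy, and/or breast feeding". The same item continues: "All female subjects will complete a urine pregnancy test at the intake visit and preceding all brain stimulation sessions". Women who report that they cannot become pregnant "will not be required to complete the pregnancy tests".
- The Note under the tDCS-related exclusions gives the reason, "although there is no known risk of tDCS to the fetus, the issue has not been fully addressed", and the rule, "Consequently, pregnant women will be excluded". It adds that women of childbearing age "will complete a pregnancy test prior to each tDCS session".
- Section 5, Vulnerable Populations, says that "pregnant women or prisoners are not included in this research study".

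The procedure also appears in three places. Item 2 of the Intake (week -1) list and item 1 of the list of steps before the tDCS period both have the woman perform the screen on her own. Both address their advice against participation to women who believe they are pregnant. The Urine Pregnancy Test paragraph under Screening/Covariates repeats the advice and instructs participants to "administer the pregnancy test independently and will inform study staff if they would like to continue participation after they have administered the pregnancy screen". It then assures them that stopping at that point carries no penalty and that travel will still be reimbursed.

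**The concern.** An exclusion criterion and the test placed next to it should lead to the same decision. Here the criterion leaves no choice, while the procedure leaves the decision with the participant once she knows her result. Staff are told what she wants to do. They are not told what the test showed, or what to do if it was positive.

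At stake is a participant-safety precaution and the consistent application of an eligibility rule. A precaution against an unresolved fetal risk works only if it is applied when the test turns positive. No statistical property of the trial is at stake: the point does not touch power, alpha or the estimand.

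**Working it through.** The plan states no figure to reproduce. The check is a comparison of the texts, with one count.

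**1. Exclusion and procedure side by side**

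| Question | Exclusion text (Medical/Neuropsychiatric item 1; tDCS-related Note; Vulnerable Populations) | Procedure text (Intake item 2; pre-tDCS item 1; Urine Pregnancy Test) |
|---|---|---|
| Who may not take part? | Pregnant women, no exception | Nobody is barred; pregnant women are advised against it |
| What do staff learn? | Not addressed | Whether she wishes to go on |
| What follows a positive test? | Exclusion, by implication | Not stated |

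Section 5, Tissue Specimens, mentions urine collection for the screen but describes no staff reading and no action on the result.

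**2. How the plan treats other tests**

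- Breath alcohol of 0.01 or more at intake: ineligible.
- An estimated IQ below 85 on the Shipley scale: ineligible.
- Carbon monoxide at Session 1: a threshold must be met to take part.
- Breath alcohol at the tDCS visits: left to the Principal Investigator's discretion.
- Carbon monoxide at intake: a level is given, but the procedure text states no consequence.

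The picture is mixed, so pregnancy is not the only test without a fixed consequence. The comparison does show that the plan writes a binding rule for some tests. It writes none for this one, although the underlying exclusion is unconditional.

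**3. Following one positive test through the written steps**

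Suppose the test first turns positive before a stimulation session.

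- She tests alone and hears the advice. If she withdraws, the exclusion is met.
- If she says she wishes to continue, the remaining pre-session steps follow: breath alcohol, carbon monoxide and questionnaires.
- Under tDCS Training Procedures, staff then confirm that nothing bearing on eligibility has changed. If she discloses the pregnancy here, the exclusion applies.
- If she does not, stimulation can begin with every written step carried out.

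For a positive test at intake, the medical history form completed with staff and reviewed for contraindications is a further opportunity for disclosure. Neither check is linked to the test result.

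**4. How often the gap occurs**

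Test points: 1 at intake + 3 sessions = 4. General eligibility checks before stimulation: 3, one per session. Tests with a stated consequence for a positive result: 0 of 4.

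**The case against.** The strongest reply is that the two sets of text do different jobs. The exclusion criteria decide eligibility; the Urine Pregnancy Test paragraph describes how the kit is used and offers a private, no-penalty exit. Wanting to continue is not the same as being eligible, and no sentence says that a woman with a positive test may be stimulated. The pre-session eligibility check and the intake medical history review both cover pregnancy, because it is one of the criteria. If both are done, a breach requires non-disclosure, and several other exclusions also rest on self-report.

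Much of this stands. The checks are real safeguards, and reliance on self-report is not in itself the complaint. What the reply does not supply is a consequence for the test. A test repeated four times beside an absolute exclusion should say what a positive result means, and the only instruction staff have at that point is to hear her wish.

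Two stronger readings are tempting, and the documents do not support either.

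- A reader might infer that the protocol authorizes stimulating pregnant women, or that some were stimulated. It does neither: three statements exclude them, and no positive test is reported.
- A reader might multiply sessions by minutes (3 × 20 = 60) and present the result as the exposure at stake. That is a hypothetical maximum in an active arm. It requires her to continue without disclosure at every session, and the documents give no basis for its probability.

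The available text is also incomplete. Consent pages were removed, and the text breaks off later within Screening/Covariates. The finding is therefore that no available section links a positive test to ineligibility. The pregnancy-test paragraph itself is intact.

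**Conclusion.** The point holds as an inconsistency of wording with a safety purpose. Pregnancy is excluded outright, the test meant to serve that exclusion is advisory at all four test points, and enforcement rests on voluntary withdrawal or disclosure. The existing checks narrow the gap but do not close it.

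Its weight is modest, for three reasons. The plan itself says no fetal risk of tDCS is known. No number of affected women can be given, because neither women of childbearing potential nor positive tests are counted. The futility paragraph reports a conditional power of 0.13 against a 20% criterion and concludes that the study should be abandoned, so any benefit is confined to remaining enrollment or reuse of the procedure.

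The conclusion assumes that the removed consent pages and lost text contain no rule on a positive test. If they do, the remaining task is to carry that rule into the procedure sections.

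**What to change.** In Intake item 2, item 1 of the pre-tDCS list and the Urine Pregnancy Test paragraph, replace the advisory sentence with a statement that a positive test makes the participant ineligible and that stimulation does not proceed. In tDCS Training Procedures, have the existing eligibility check ask each non-exempt woman to confirm verbally, before stimulation, that her test was negative.

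Keep private testing, no-penalty withdrawal, travel reimbursement and the exemption for women who cannot become pregnant. Staff need not read the test, and no new data field is needed. With exempt women set aside, a recorded field that could read no would come close to disclosing a pregnancy. Section 4, Subject Privacy/Protected Health Information, opens study data to the IRB, authorized university staff and the FDA, and section 6 allows for university employees and students among the participants.

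The cost is revised wording in four places and one spoken question at three existing checks, with no new test, visit or staff. The downsides are a small loss of privacy and continued reliance on the woman's own report.

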**Figure 1.**

## DRUGS OR DEVICES

## Transcranial direct current stimulation (tDCS) and sham stimulation.

## STUDY PROCEDURES

## 1. Procedures

**Telephone Screening:** Potential participants will be screened by an experienced research technician to determine initial study eligibility. If the subject meets preliminary telephone eligibility criteria he/she will be invited to attend a 3 hour Intake visit.

**Visit Reminders:** Participants will receive study visit reminders 24 – 48 hours prior to their scheduled study visits via phone call, email or text (participants who provide a cell phone number for contact).

**Intake (week -1):** (Visit duration: ~3 hours). Participants will:

1. Hear a study description where all study procedures will be reviewed. Participant questions will be answered. Following this presentation, the combined informed consent and HIPAA form will be completed;
2. Women of childbearing potential will be provided with a urine pregnancy screen and will be instructed to perform the screening independently Participants will be instructed that women who think they are pregnant are advised not to participate in the study;
3. Perform a BrAC assessment to control for alcohol consumption. Participants with a BrAC greater than or equal to 0.01 at Intake Visit will be ineligible;
4. Perform a carbon monoxide (CO) breath assessment to confirm ( $CO \geq 10$  ppm) tobacco exposure;
5. Complete a brief medical history form with a trained staff member;
6. Complete Shipley Institute of Living Scale (SILS) IQ test. Participants earning less than an estimated WAIS-R IQ score of 85 will be ineligible;
7. Complete demographics and smoking history (smoking rate, nicotine dependence, Cigarette Brand Form, brief QSU), G-FCQ-S, ETOH, and cognitive tasks (see Measures table);
8. Provide one 2ml saliva sample for DNA collection and genotyping (Oragene™) and a 5ml saliva sample for nicotine metabolite assay. These saliva samples are voluntary for study participation.

**tDCS Sessions:** (Visit duration ~3 hours). The stimulation protocol is adapted from IRB protocol 809185 (Transcranial Direct Current Stimulation Investigations of Cognition and Action), which was employed in The Laboratory for Cognition and Neural Stimulation (LCNS) and protocols 820231, 819023 & 820371 at CIRNA.

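### The days-of-abstinence model omits intake CO and baseline cigarettes per day, which may cost precision and leaves chance imbalance in them unadjusted

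*Combined protocol and SAP*

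**What the plan says.** The analysis text at the end of 1. Screening/Covariates describes the abstinence analysis in one sentence: "Similar models were used to estimate the effects of dose group on total number of days of biochemically-verified abstinence during the monitored abstinence period". It then closes the covariate list: "age, sex, race, and nicotine dependence (FTND score) were included as covariates". Table 1 places days of biochemically confirmed abstinence under Primary Outcomes.

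The two values in question are both taken at Intake:

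- **CO.** Item 4 of the Intake list in 1. Procedures reads "Perform a carbon monoxide (CO) breath assessment to confirm", with 10 ppm as the lower limit.
- **Smoking rate.** Item 7 reads "Complete demographics and smoking history (smoking rate, nicotine dependence, Cigarette Brand Form, brief QSU". In Table 1 the row "Time Line Follow Back (TLFB), CO" is marked at Intake, at the tDCS sessions and at the monitoring visits.

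Neither is described as voluntary, whereas the saliva samples are. Section 2. Design puts random assignment after the Intake Visit, so both are true baseline values.

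Under Monitoring Visits, an abstinent day is one that the participant reports as abstinent and that CO confirms. The CO rule differs by day. For the first visit: "On Day 6, a CO reading of less than 10ppm or less than 50% of CO breath sample taken at the Intake session" is enough. For the rest: "On Days 8, 10, and 12, a CO reading less than 8 ppm will be considered as biochemically-confirmed abstinence".

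**The concern.** The outcome combines a smoking report with a CO reading. The trial holds the baseline value of each, yet the model uses neither and relies on FTND to represent smoking intensity. FTND probably carries some of the same information, but it is neither a measured CO nor a daily cigarette count, and the available text gives no reason for using it instead of, rather than alongside, those values.

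Two things could be lost. If the omitted values predict abstinence beyond age, sex, race and FTND, the interval for the dose effect is wider than it needs to be. If the three arms happen to differ on those values, nothing in the listed model corrects for it. For intake CO the second point has an extra edge, because a high intake value relaxes the Day 6 criterion. An arm with more high-CO participants would face an easier Day 6 test on average.

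**Working it through.** **1. The plan's own figures.** The text gives no power, sample size or SD for the abstinence model. The only power figure is the conditional power of 0.13 in the futility paragraph, which comes from the mixed model and is not tied to this analysis. It cannot be checked directly because the information fraction t is not given. It is attainable:

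- CP = Φ[(z₁√t + θ(1−t) − z_α)/√(1−t)], with z₁ = 0.04 from the text.
- Assuming two-sided 0.05 and 80% power, z_α = 1.96 and θ = 2.802. CP = 0.13 then needs t of about 0.57.

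Nothing below depends on this.

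**2. Precision.** The inputs are:

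- d = 0.45, the design effect size quoted in the futility paragraph. Carrying it over to abstinence days is an assumption.
- Two-sided alpha 0.05, 80% target power and sham to pooled active 1:2, all assumed. These give 59 + 118 = 177 participants, which is an illustrative base and not the trial's sample size.
- R², the share of residual variance that the two added terms explain beyond the four listed covariates. The documents do not give it, so a range is shown.

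For a linear model, the standard error is multiplied by √(1−R²), the effective sample size is multiplied by 1/(1−R²), and

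power = Φ[0.45 × √(59×118/177) / √(1−R²) − 1.96].

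Here √(59×118/177) = 6.272 and 0.45 × 6.272 = 2.822. With R² = 0, power is Φ(0.862) = 80.6%.

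| Assumed R² | SE multiplier | Gain in effective N | Power | Total N for 80% |
|---|---|---|---|---|
| 0 | 1.000 | 0% | 80.6% | 177 |
| 0.01 | 0.995 | 1.0% | 81.0% | 174 |
| 0.05 | 0.975 | 5.3% | 82.5% | 168 |
| 0.10 | 0.949 | 11.1% | 84.5% | 159 |
| 0.20 | 0.894 | 25.0% | 88.4% | 141 |

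The gain runs from negligible to useful, and the documents do not show where in this range the trial lies.

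**3. Reach of the CO-linked rule.** A Day 6 reading passes if it is below 10 ppm or below half the intake value, so the cut-off is max(10, 0.5 × intake CO).

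| Intake CO (ppm) | Day 6 cut-off (ppm) |
|---|---|
| 10 | 10 |
| 20 | 10 |
| 24 | 12 |
| 30 | 15 |
| 40 | 20 |

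A Day 6 reading of 12 ppm passes for someone who entered at 30 ppm and fails for someone who entered at 20 ppm. Intake CO changes the classification only when three conditions hold together: intake CO exceeds 20 ppm, the Day 6 reading is at least 10 ppm but under half the intake value, and the participant reports abstinence. The documents do not say how many participants that describes. On Days 8, 10 and 12 the cut-off is a fixed 8 ppm, so intake CO plays no part in three of the four visits.

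**The case against.** The strongest reply is that this is a covariate preference and not an error. The arms are randomised, the model already adjusts for a dependence score, and no stated rule is broken. That stands. A reader might infer that the omission biases the dose comparison, but randomisation balances intake CO and smoking rate in expectation, so the cost is confined to precision and chance imbalance.

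Second, the loss of precision is not demonstrated. It depends on prognostic value beyond FTND, for which there is no figure, and at R² = 0.01 it is trivial. That also stands: the most that can be said is that precision may be lost.

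Third, the model cannot be seen. The text breaks off just before the sentence on abstinence, so what the similar models are is unknown. A count of days within a 7-day attempt is bounded, and the model may not be linear. The variance formulas above would then not carry over, and adding a prognostic term could change the effect being estimated. It would therefore be too strong to say that adjustment costs nothing and cannot bias.

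Fourth, a covariate leaves the Day 6 definition as it is, and one straight slope does not match a cut-off that is flat to 20 ppm and then rises. This is correct. Only re-scoring Day 6 against a single fixed analysis cut-off would test the definition itself.

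Fifth, the analysis is written in the past tense and a futility result is reported, so covariates chosen now come after results were known. This limits the status of the fix but does not remove its use.

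**Conclusion.** The point holds at modest weight. The listed model for a Table 1 primary outcome leaves out two pre-randomisation values that are scheduled for everyone and correspond directly to the outcome's components. This may give up precision and leaves chance imbalance unadjusted. Under the assumptions stated (linear model, 80.6% base power, R² of 0.01 to 0.20), the gain in power from adding them is between about 0.4 and 8 percentage points (81.0 − 80.6 and 88.4 − 80.6). The true value is unknown.

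Two stronger readings are not supported. One is that the outcome as a whole depends mechanically on intake CO; it does so at one visit of four, and only above 20 ppm. The other is that the futility conclusion would have come out differently; the documents do not connect that calculation to this model, and no such claim is made here.

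**What to change.** Add intake CO and cigarettes per day from the Intake TLFB, both as continuous terms, to age, sex, race and FTND in the days-of-abstinence model.

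If results have already been seen, as the past tense suggests, keep the model with the four listed covariates in its place. Report the extended model beside it as a sensitivity analysis labelled as added after the fact. State the model form and, if it is non-linear, say that the adjusted effect may be a different estimand.

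The cost is a line or two of analysis text, two degrees of freedom and no new data. The downside is the post hoc status if the terms are added now.
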